## **7.4 Administration/handling of the trial drugs**

### **7.4.1. Handling, storage and supply**

Study drug(s) will be delivered to pharmacy and labelled according to the terms of the trial's MHRA approval.

### **7.4.2. Administration of the trial drugs**

Golimumab (Simponi®) should be injected subcutaneously once every four weeks.

In patients weighing 100 kg or more at baseline, the starting dose of golimumab will be 100 mg four weekly to be continued for the duration of the interventional period (week 0 to 24), even in cases of subsequent intentional weight loss.

In these cases, the investigators, taking into account the increased risk of certain serious adverse drug reactions with the 100 mg dose compared with the 50 mg dose (see [section 7.7](#) and [section 7.8](#)) will perform regular monitoring as specified in the summary schedule of study assessments ([section 8.6](#)).

The IMP will be administered by a suitably qualified and authorised member of the research team (i.e. study doctor or nurse) in an outpatient clinic setting within The Leeds Teaching Hospitals NHS Trust.

## **7.5 Prior and concomitant illnesses**

Any concomitant diseases not included in the exclusion criteria are to be controlled using appropriate medication before the patient enters the study and if medically appropriate, the medication is to be continued during the entire study period. Concomitant medical conditions, any relevant medications, and any changes to both of these will be documented appropriately in the eCRF. Any new illness or worsening of a previous medical condition is to be recorded as an AE.

## **7.6 Prior and concomitant medications**

### **7.6.1. Prohibited prior medications**

Prohibited prior medications are listed on the exclusion criteria.

### **7.6.2. Permitted concomitant medications**

All concomitant medication taken during the study must be recorded on the source data worksheets. Treatment with concomitant PsA and coexisting Pso therapies during the study is permitted only as outlined in the exclusion criteria ([section 6.3.2](#) and [section-6.3.3](#)) and described in the paragraphs below. Patients taking permitted medication should be on chronic stable doses at the baseline visit (week 0).

The following medications will be permitted during the interventional period (week 0 to 24):

#### **1. Folic Acid**

All patients will receive folic acid prophylaxis with generic 5mg tablets 6 days/week given orally (except day of methotrexate). Folic acid will be supplied locally by the Trust's pharmacy.

#### **2. Corticosteroids**

Period 1 (Double blind randomised phase): Both groups will receive corticosteroids at baseline up to a dose of 120 mg methylprednisolone (unless contraindicated or not tolerated). This will be performed

either as a stat bolus intra-muscular injection (if  $\geq 4$  swollen joints) or as intra-articular injections (to a maximum of 4 joints injected per visit; 20-80mg per joint with the remainder, if appropriate, given as an intra-muscular injection). In addition, any swollen joint observed at subsequent visits (only at either week 8 or at week 12) may be injected with methylprednisolone (20-80 mg per joint) to a maximum dose of 120 mg methylprednisolone into a maximum of four joints between both visits. In case of  $\geq 4$  swollen joints at either week 8 or at week 12, a dose of methylprednisolone 120 mg IM could be administered instead of intra-articular injections. Any injections at baseline will ONLY be done after the baseline US and WB-MRI scan has been performed. No corticosteroid injections will be allowed between weeks 12 and 24. Other limitations apply as outlined in [section 7.3](#).

**Use of oral corticosteroid will not be permitted until week 24.**

Period 2 (Observational phase): use of steroids will be permitted after completion of trial-related procedures pertaining to week 24. Patients will be allowed to receive up to 240 mg IM or IA corticosteroid injections if the investigator deems that there is still on-going disease activity until the end of the study period and unless a clinical or imaging assessment is scheduled within the following 6 weeks. The joint(s) injected must be recorded along with the medication taken on the examination section of the corresponding eCRF.

**3. NSAIDs**

Patients will be permitted to be on non-steroidal anti-inflammatory drugs (NSAIDs) for the duration of the study. Every effort should be made to maintain stable doses of concomitant NSAIDs during the study. In the event of tolerability issues, the NSAID dose may be decreased or discontinued, with the substitution of another NSAID. Data will be collected on NSAID use throughout the trial. NSAIDs should not exceed the maximum recommended dose and patients should be on only one NSAID at a time.

**4. Analgesics**

Simple analgesics with no anti-inflammatory action may be used.

**5. Aspirin**

Aspirin at daily doses of up to 150 mg is permitted if indicated for cardiovascular protection.

Any concomitant diseases not included in the exclusion criteria are to be controlled using appropriate medication before the patient enters the study and, if medically appropriate, the medication is to be continued during the entire study period. Concomitant medical conditions, any relevant medications, and any changes to both of these will be documented appropriately in the eCRF. Any new illness or worsening of a previous medical condition is to be recorded as an AE.

**After the first 24 weeks** (Period 2: Observational phase phase), the addition of DMARDs will be allowed at the discretion of the investigator if it is thought that there is on-going disease activity.

During the double-blind treatment period (week 0 to week 24) any dose adjustment, changes of NSAIDs, and/or introduction of a new NSAID is not permitted, unless required for safety reasons or for rescue therapy.

**7.6.3. Prohibited concomitant medications**

The following therapies will NOT be permitted during the interventional period (week-0-baseline-visit to week 24):

- PsA and coexisting Pso therapies that are defined as prohibited in the exclusion criteria.

- Any therapy within the washout periods specified in the exclusion criteria (see exclusion criteria 17, [section 6.3.3](#)).
- Live vaccines (including BCG)

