## 6.3 Eligibility criteria

### 6.3.1. Inclusion criteria

Patients meeting all of the following criteria will be considered for enrolment into the study:

INCL1.	Male and female patients aged $\geq 18$ years at the time of signing the Informed Consent Form.
INCL2.	Subjects with a diagnosis of psoriatic arthritis as per the Classification for Psoriatic Arthritis (CASPAR) criteria (see appendix 3 ) confirmed up to 24 months prior to screening.
INCL3.	Subjects with active PsA defined as the presence of at least 3/78 tender and at least 3/76 swollen joints (see section 8.2.3 and section 8.2.4 ) or 2 swollen and 2 tender joints plus one affected entheseal site (Achilles tendon and/or plantar fascia) at baseline.

INCL4.	Are capable of understanding and signing an informed consent form.
INCL5.	Women of childbearing potential or men capable of fathering children must be using adequate birth control measures (e.g.: abstinence, oral contraceptives, intrauterine device, barrier method with spermicide, surgical sterilization) during the study and for 6 months after receiving the last administration of study agent. Female subjects of childbearing potential must test negative for pregnancy. Female subjects must agree to not donate eggs (ova, oocytes) during the study and for 6 months after last dose of study agent. Male subjects must agree to not donate sperm while in the study and for 6 months after last dose of study agent.
INCL6.	Patients fulfilling the following TB criteria:
INCL6.1.	Have no history of latent or active TB prior to screening. An exception is made for subjects with a history of latent TB and documentation of having completed appropriate treatment for latent TB 3 years prior to the first administration of study agent. It is the responsibility of the investigator to verify the adequacy of previous antituberculous treatment and provide appropriate documentation.
INCL6.2.	Have no signs or symptoms suggestive of active TB upon medical history and/or physical examination.
INCL6.3.	Have had no close contact with a person with active TB or, if there has been such a contact, will be referred to a physician specializing in TB to undergo additional evaluation, and if warranted, receive appropriate treatment as if having latent TB prior to or simultaneously with the first administration of study agent.

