### 6.3.2. Exclusion criteria

Patients fulfilling any of the following conditions or characteristics will be excluded from study enrolment:

EXCL 1.	Previous treatment with any conventional or biological DMARDs, where “treatment” is defined as a therapeutic dosage according to each product’s SmPC. Topical preparations for psoriasis are not considered DMARDs (examples include, but are not limited to, steroids, salicylic acid, tar).
EXCL 2.	Any chronic inflammatory arthritis diagnosed before 16 years old.

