EXCL17.	Patients who have received any systemic/intra-articular corticosteroids within 4 weeks prior to screening. Topical preparations with steroids for cutaneous use, or inhalers for the treatment of asthma are not considered systemic/intra-articular corticosteroids.
EXCL18.	Patients with a history of confirmed blood dyscrasia.
EXCL19.	Patients with a history of mental illness that would interfere with their ability to comply with the study protocol.
EXCL20.	Patients with a history of drug and/or alcohol abuse that would interfere with their ability to comply with the study protocol.
EXCL21.	Patients with a history of any viral hepatitis within 1 year of screening
EXCL22.	Patients who have received or are expected to receive any live virus or bacterial vaccinations or treatments that include live organisms (eg. a therapeutic infectious agent such as BCG that is instilled into the bladder for the treatment of cancer) within 3 months prior to the first administration of study agent, during the trial, or within 6 months after the last administration of the study agent.
EXCL23.	Patients who demonstrate Hypersensitivity to the IMP's active substance, or any of the excipients detailed in the SmPC.

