### 7.3 Non-Investigational Medicinal Product (NIMPs)

Within the trial treatment intervention, the following are classed as Non-Investigational Medicinal Product (NIMPs):

- **Methotrexate**

Methotrexate will be administered orally in both treatment arms at a starting dose of 15mg weekly. If tolerated, it will be increased to 20mg and 25mg weekly at weeks 2 and 4 respectively in both treatment arms.

Subcutaneous MTX may be administered if intolerance to oral MTX is observed.

MTX will be prescribed by the research team and supplied by the hospital pharmacy.

- **Corticosteroids: methylprednisolone**

Both groups will receive corticosteroids at baseline up to a dose of 120 mg methylprednisolone (unless contraindicated or not tolerated). This will be performed either as a stat bolus intra-muscular injection (if  $\geq 4$  swollen joints) or as intra-articular injections (to a maximum of 4 joints injected per visit; 20-80mg per joint with the remainder, if appropriate, given as an intra-muscular injection). The steroid dose administered per joint will be as follows: 80 mg for shoulders, knees or hips; 40 mg if ankles, wrists or elbows; 20 mg if small joints of hands or feet.

Oral steroids (regardless of the indication) are not allowed until week 24. Failure to comply will result in withdrawal from trial medication ([section 7.10](#)). The use of other forms of steroids until week 24 is restricted (as mentioned in exclusion criteria 17, [section 6.3.3](#) of this protocol).

After the completion of trial-related procedures pertaining to week 24, any form of steroid is allowed in accordance to indication and national/local guidance.

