Biochemistry (including CRP) / Haematology, ESR	X	X	X	X	X	X	X	X	X	X	X	X	X	
Immunology tests  : ANA (including dsDNA) anti-CCP and RF	X										X	X	X	
Blood and urine collection for biomarkers (Biological Sub-study)		X			X			X		X	X	X	X	
Urinalysis 	X													
Pregnancy test 	X													
Whole-Body MRI (WB-MRI) 	X							X		X		X 	X 	

Study Period	Period 1: Double-blind randomised									Period 2: Observational*				Withdrawal visit **
	Screen	Baseline	(Safety)	(Safety)	Secondary outcome	(Safety)	(Safety)	Primary outcome	(Safety)	Secondary outcome	End of study visit	Extra Visit		
Study Phase														
Week	-4 to 0	0	4 (±7 days)	8 (±7 days)	12 (±7 days)	16 (±7 days)	20 (±7 days)	24 (±7 days)	28 (±7 days)	36 (±7 days)	52 (±7 days)	Y***	X	
Visit number	1	2	3	4	5	6	7	8	9	10	11	98	99	
Musculoskeletal US scan 	X				X			X		X		X 	X 	
Chest-X-ray  , ECG	X													
Plain X-ray of Hands and Feet 	X													
X-ray of the orbits 	X													
Physician VAS global disease Activity	X	X			X			X		X	X	X	X	
Physician Likaert scale, articular disease Activity	X	X		X	X			X		X	X	X	X	
Patient VAS global disease Activity	X	X			X			X		X	X	X	X	
Patient VAS articular pain	X	X			X			X		X	X	X	X	
Patient Likaert scale, articular disease Activity	X	X		X	X			X		X	X	X	X	
HAQ	X	X			X			X		X	X	X	X	
DLQI	X				X			X		X	X	X	X	
SF-36	X	X			X			X		X	X	X	X	
ASQoL	X				X			X		X	X	X	X	
BASDAI		X			X			X		X	X	X	X	
Administration of SC IMP 		X	X	X	X	X	X	X						

**1.** At screening visit; end of study visit (visit 11, week 52); extra visit (week Y); and withdrawal visit (week X), immunology tests should not be repeated if results available within 20 days prior to study visit.

If subjects do not have a chest x-ray or hands/feet x-ray performed within 3 months of screening, an x-ray should be performed after it is certain the subject meets the inclusion/exclusion criteria (in order to minimize exposure to x-ray radiation).

X-ray of the orbits should be performed only in subjects contraindicated to WB-MRI, who report a personal history suggestive of metallic fragments present in the orbits.

**2, 3.** Urinalysis and Pregnancy test can be repeated in other visits as clinically indicated.

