## APPENDICES

### **APPENDIX 1: Definition of Women of Childbearing Potential (WCBP)**

A woman of childbearing potential (WCBP) is defined as one who is biologically capable of becoming pregnant. This includes women who are using contraceptives or whose sexual partners are either sterile or using contraceptives. Sexually active women participating in the study must use a medically acceptable form of contraception during the study and for 6 months after the last dose of study medications. Medically acceptable forms of contraception for women include oral contraception, injectable or implantable methods, intrauterine devices, or properly used barrier contraception.

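### Section 7.6.3 ends the live-vaccine ban at week 24, although EXCL22 sets a window to 6 months after the last dose (about week 50, or week 46 if the last dose is at week 20)

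*Protocol*

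**What the plan says.** Protocol section 7.6.3 introduces its list with "The following therapies will NOT be permitted during the interventional period (week-0-baseline-visit to week 24", and the last item is "Live vaccines (including BCG").

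EXCL22, in section 6.3.3, concerns patients who have had or expect to have live vaccines or treatments containing live organisms. Its window starts 3 months before the first dose and continues "during the trial, or within 6 months after the last administration of the study agent". The exclusion list is introduced in section 6.3.2 as a set of entry conditions: "Patients fulfilling any of the following conditions or characteristics will be excluded from study enrolment".

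The timing of the last dose is not settled. In section 8.6 the row "Administration of SC IMP" has seven marks, from baseline to week 24, and section 8.13 lists dispensing of study drug at week 24. Section 8.18 says that injections are discontinued in both arms at week 24, and section 5.1 says the same of golimumab. That can be read as a last dose at week 20.

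Section 7.10.1 makes the giving of disallowed drugs a withdrawal criterion and points to 7.6.3 for what is disallowed. Section 7.7 refers the reader to the SmPC for warnings and precautions.

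**The concern.** The two sections give different end dates for the same hazard. EXCL22 reaches 6 months past the last dose. The on-study list stops at week 24, which may be the day of the last injection.

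The patient at issue is one who was properly enrolled, with no live vaccine in prospect, and who first needs one after week 24, for instance for unplanned travel. Site staff who look up what is disallowed find a list that has expired. They would have to decide for themselves whether an entry criterion still binds. Allocation is requested from pharmacy only before analysis (Protocol 11.10), so short of emergency unblinding they would not know whether the patient had received golimumab. What is at stake is patient safety and consistency within the protocol, not any estimate or test.

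**Working it through.** **Inputs**

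- End of the on-study ban: week 24 (Protocol 7.6.3).
- End of the post-dose window: last dose plus 6 months (EXCL22).
- Dosing every 4 weeks, visits within 7 days of target (Protocol 8.6).
- Last dose in a patient who completes treatment: week 24 (8.6, 8.13) or week 20 (one reading of 5.1 and 8.18).
- Conversion: 6 months = 365.25 / 2 / 7 = 26.09 weeks, taken as 26.

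**Formulae**

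End of window = last-dose week + 26. Gap = end of window − 24.

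| Last dose (week) | Window ends (week) | Gap after week 24 (weeks) |
|---|---|---|
| 24 | 24 + 26 = 50 | 26 |
| 20 | 20 + 26 = 46 | 22 |
| 16 | 16 + 26 = 42 | 18 |
| 12 | 12 + 26 = 38 | 14 |
| 8 | 8 + 26 = 34 | 10 |
| 4 | 4 + 26 = 30 | 6 |
| 0 | 0 + 26 = 26 | 2 |

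With the 7-day visit window, a week-24 dose falls between weeks 23 and 25, so its window ends between weeks 49 and 51. A week-20 dose falls between weeks 19 and 21, giving weeks 45 to 47. Under either reading the window outlasts week 24. Even a patient who had only the baseline dose has a gap of 2 weeks.

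**Does other protocol text close the gap?**

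- *Carry-over of exclusion criteria.* Where the protocol wants an exclusion criterion to act on study, it can say so. For steroids, section 7.3 states: "The use of other forms of steroids until week 24 is restricted (as mentioned in exclusion criteria 17". Section 7.6.3 cites the same criterion for washout periods. Neither section cites EXCL22. Section 7.6.2 carries exclusion limits forward for arthritis and psoriasis therapies, not for vaccines.
- *The other 6-month window.* INCL5 requires contraception "during the study and for 6 months after receiving the last administration of study agent". Appendix 1 repeats this as a duty for sexually active women, who "must use a medically acceptable form of contraception during the study and for 6 months after the last dose of study medications". It does not repeat the duties on men or on egg and sperm donation. So the protocol restates one post-dose duty outside the eligibility list, but only in part.
- *Visit lists.* The lists for weeks 24, 28, 36 and 52 and for the withdrawal and flare visits contain no vaccine check.
- *Scope.* EXCL22 also names treatments that contain live organisms. The item in 7.6.3 names live vaccines only.

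**The case against.** The best defence is that week 24 marks the scope of a list, not the end of a hazard. Section 7.10.1 uses 7.6.3 as a trigger for withdrawal, and it sits under the heading on withdrawal of trial treatment. Once injections have stopped there is no study drug to withdraw, so a list that ends at week 24 is logical. This reading is plausible and shapes the fix: simply extending the 7.6.3 list would create a withdrawal trigger in the observational phase with no clear meaning. It does not remove the conflict, because no other visible line takes over after week 24.

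A second defence is that EXCL22 already states the window and can be read as continuing. It does screen out foreseeable cases. But it is framed as a condition of enrolment and turns on what is expected, so it does not clearly govern a need that arises later.

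Third, the SmPC, consent pages and GP letter may already bar live vaccines. That stands, and it limits the point to the protocol text.

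A reader might infer more than the documents support:

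- That live vaccines are permitted in the observational phase. Nothing says so; the list is silent.
- That the contraception rules prove an oversight. Appendix 1 covers only sexually active women, and some other post-dose duties rest on eligibility text alone, so the contrast is only suggestive.
- That the ban must run to week 52. EXCL22 does mention the trial period, but for a patient who had only the baseline dose this would add 52 − 26 = 26 weeks beyond the 6-month point.

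**Conclusion.** The point holds as a minor safety-consistency correction. The end date in 7.6.3 falls inside the protocol's own window, by 26 or 22 weeks in patients who complete treatment and by 2 to 18 weeks in those whose last dose was between baseline and week 16. No visible protocol line clearly bars a live vaccine needed for the first time after week 24.

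This rests on 6 months being 26 weeks, on EXCL22 being an entry criterion, and on the supplied text alone. Confidence is medium, because documents not available here may already cover the point. The protocol and SAP give no live-vaccination rate, so no number of affected patients can be stated. Sample size and the week-24 analysis are unaffected.

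**What to change.** Keep the week 0 to 24 list in 7.6.3 as the trigger that 7.10.1 uses. Add a separate sentence, for example:

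*In both arms, live vaccines and treatments containing live organisms (as in EXCL22) are not permitted until at least 6 months after the patient's last administration of study agent. A breach after study injections have stopped is recorded as a protocol deviation and followed for safety; it does not lead to withdrawal from observation.*

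Add a reminder to the week-24 and withdrawal visit lists. Extending the ban to week 52 for patients who stop early is optional and a matter for the sponsor and investigator.

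The cost is a short addition to 7.6.3 and two reminders. Recording of concomitant medication (7.6.2) and follow-up to week 52 (7.10) are already in place.

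Follow-up is probably complete: SAP 5.2 holds the final analyses until the last week-52 visit, and SAP 3.2.4 was written after unblinding. In that case, list any live vaccines recorded within 6 months of the last dose from the concomitant-medication data. The listing will be only as complete as the recording of vaccines there.

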#### 7.6.4. Surgical procedures

Planned surgery within the study period which is expected to require omission of any study medication of 28 days or more will not be permitted during the course of the study.

### 7.7 Special warnings and precautions for use

Please consult the SmPC for further details.

### 7.8 Dose modifications

Patients will receive 50mg of golimumab unless at the time of baseline they are 100 kg of weight or over (see also [section 7.4](#)) In this case they will be eligible for 100mg golimumab. Golimumab dose will not be altered throughout the interventional period of the trial (week 0 to 24).

### 7.9 Assessing subject compliance with trial treatment(s)

Every attempt will be made to select patients who have the ability to understand and comply with study instructions. The investigator is responsible for discussing methods to ensure high treatment compliance with the patient before randomization.

If a patient is noncompliant with any study procedure, the investigator should assess the patient to determine the reason and educate and/or manage the patient as appropriate to improve compliance. Specific instances of non-compliance to trial treatment, which would result in withdrawal, are mentioned in [section 7.3](#).

